11.0 Participant Disposition

The number and percentage of participants dosed, and members of each analysis set will be presented. The number and percentage of participants who withdrew from the study prematurely and a breakdown of the corresponding reasons for withdrawal will also be presented.

12.0 Protocol Deviations and Violations

Protocol deviations will be listed.

13.0 Demographic and Baseline Characteristics

13.1 Demographics

All demographic data as collected during the screening visit will be listed by participant.

EDSREP 009 T 01 G Page 10 of 30

OCON

Statistical Analysis Plan GBT2180A-2180AX Protocol: GBT021601-013 Version Date: 01-May-2023

Participant demographics will be summarized descriptively for all participants. The summary will include the participants' age (in years), gender, race, ethnicity, weight (in kg), height (in cm), and body mass index (BMI) (in kg/m²) measured at screening. Demographics will be summarized for the safety and PK sets, if they are different.

13.2 Medical History

Medical history, categorized by preferred term according to Medical Dictionary for Regulatory Activities (MedDRA) (Version 25.0), will be listed.

13.3 Other Baseline Characteristics

The results of drug and alcohol screen at screening and baseline will be listed.

The results of serology at screening will be listed.

The results of SARS-CoV-2 tests will be listed.

The results of pregnancy tests (beta-human chorionic gonadotropin β -HCG) and follicle stimulating hormone (FSH) test results will be listed.

Non-compliance to in- or exclusion criteria (if any) will be listed.

14.0 Concomitant Medications

Concomitant medications, categorized by medication group and subgroup according to WHO Drug Dictionary (Version WHO Drug Global B3 SEP2022), will be listed.

Medications with an end date prior to the dose of study drug will be considered prior medications and will be noted in the listing. Concomitant medications are defined as those taken by the participant at any time between the date of study drug administration and study completion/discontinuation. Medication with start date being partially or completely missing will be assumed to be concomitant if it cannot be definitively shown that the medication did not occur during treatment. Any ongoing medications, either with a start date before study drug administration or during the study period, will be reported as concomitant medication.

15.0 Treatment Compliance and Exposure

Exposure data will be listed by participant.

A listing of study dates (date of informed consent signature, date of medication, and follow-up) will be provided.

16.0 Pharmacokinetic Analyses

16.1 Pharmacokinetic Variables

PK concentrations will be measured in whole blood, plasma, CCI urine, feces and vomitus (if applicable).

16.1.1 Plasma, Whole Blood and CC Variables

16.1.1.1 Concentrations

- Plasma concentration of GBT021601
- Whole blood concentration of GBT021601
- CCI
- Plasma concentration of ¹⁴C-GBT021601 total radioactivity
- Whole blood concentration of ¹⁴C-GBT021601 total radioactivity

CC

EDSREP 009 T 01 G Page 11 of 30

CCI

16.1.1.2 Whole Blood, Plasma and CCI Parameters

• PK Parameters for GBT021601 and ¹⁴C-GBT021601 total radioactivity are defined in Table 4.

EDSREP 009 T 01 G Page 12 of 30

Table 4: Whole Blood, Plasma and CC Parameters

Parameter	Description	Analyte	Matrix
Cmax	Maximum observed concentration	¹⁴ C-GBT021601 Total Radioactivity, GBT021601	Whole Blood, Plasma, CC
t _{max}	Time to attain maximum observed concentration	¹⁴ C-GBT021601 Total Radioactivity, GBT021601	Whole Blood, Plasma, CC
AUC ₀₋₂₄	Area under the plasma concentration-time curve up to 24 hours postdose	¹⁴ C-GBT021601 Total Radioactivity, GBT021601	Whole Blood, Plasma, CCI
AUC _{0-t}	Area under the plasma concentration-time curve up to time t, where t is the last point with concentrations above the lower limit of quantification	¹⁴ C-GBT021601 Total Radioactivity, GBT021601	Whole Blood, Plasma, CCI
AUC _{0-inf}	Area under the plasma concentration-time curve from time 0 to infinity calculated as: AUC _{0-inf} =AUC _{0-t} +C _{last} /K _{el} , where C _{last} is the last measurable plasma concentration	¹⁴ C-GBT021601 Total Radioactivity, GBT021601	Whole Blood, Plasma, CCI
K _{el} (also denoted as λ _z)	Apparent terminal phase rate constant calculated by linear regression of the terminal log-linear portion of the concentration vs. time curve. Linear regression of at least three points and adjusted R^2 greater than 0.80 are required to obtain a reliable λ_z .	¹⁴ C-GBT021601 Total Radioactivity, GBT021601	Whole Blood, Plasma, CCI
t _{1/2}	Terminal phase half-life expressed in time units. Adjusted R ² greater than 0.80 is required to obtain a reliable $t_{1/2}$. If adjusted R ² ≤ .80 then parameter is not included	¹⁴ C-GBT021601 Total Radioactivity, GBT021601	Whole Blood, Plasma, CCI
OL /F	Apparent total clearance, calculated as dose/AUC _{0-inf}	MC CDT024504 Tatal Dadia activity	Whale Disast
CL/F	, apparent total olearande, dallourated as absentional	¹⁴ C-GBT021601 Total Radioactivity, GBT021601	Whole Blood, Plasma, CCI
V _z /F	Apparent volume of distribution at terminal phase, calculated as: $(CL/F)/K_{el}$	¹⁴ C-GBT021601 Total Radioactivity, GBT021601	Whole Blood, Plasma, CC
Ratio AUC B:P	Blood to plasma ratio based on AUC _{0-inf}	¹⁴ C-GBT021601 Total Radioactivity, GBT021601	Whole Blood, Plasma
Ratio C _{max} B:P	Blood to plasma ratio based on C _{max}	¹⁴ C-GBT021601 Total Radioactivity, GBT021601	Whole Blood, Plasma
	CCI		

EDSREP 009 T 01 G Page 13 of 30

Parameter	Description	Analyte	Matrix
	CCI		
%AUCextrap	Percentage of AUC _{0-inf} that is due to extrapolation from the time of last observed concentration to infinity.	¹⁴ C-GBT021601 Total Radioactivity, GBT021601	Whole Blood, Plasma, CCI
Adj R ²	Goodness of fit statistic for the loglinear terminal elimination phase of the concentration time profile identified by least squares linear regression and adjusted for the number of points (minimum of 3) used in the estimation of Kel	¹⁴ C-GBT021601 Total Radioactivity, GBT021601	Whole Blood, Plasma, CCI
K _{el} _Start	The start time used in the regression for the determination of Kel	¹⁴ C-GBT021601 Total Radioactivity, GBT021601	Whole Blood, Plasma, CC
K _{el} _End	The end time used in the regression for the determination of K_{el}	¹⁴ C-GBT021601 Total Radioactivity, GBT021601	Whole Blood, Plasma, CCI
K _{el} _N	The number of points used in the regression for the determination of Kel	¹⁴ C-GBT021601 Total Radioactivity, GBT021601	Whole Blood, Plasma, CC

CC

Note: AUCs will be calculated using the linear/log trapezoid rule, expressed in units of concentration x time. Additional PK parameters may be generated at the discretion of the PK specialist or the sponsor.

EDSREP 009 T 01 G Page 14 of 30

16.1.2 Urine, Feces and Vomitus (if applicable) Variables

16.1.2.1 Concentrations

- GBT021601 concentrations and amounts excreted in urine and feces
- ¹⁴C-GBT021601 Total Radioactivity, concentrations and amounts excreted in urine
- 14C-GBT021601 Total Radioactivity, concentrations and amounts excreted in feces
- 14C-GBT021601 Total Radioactivity, concentrations and amounts excreted in vomitus, if applicable.

16.1.2.2 Pharmacokinetic Amounts Excreted

Urinary and fecal PK parameters will be calculated using SAS and/or WNL. Excretions in mg equivalent (mg eq) for each interval (Ae_{t1-t2}) will be derived from the urinary and fecal concentrations and the sample collection interval volumes or weights respectively, by multiplying the concentration in the interval (C) and the volume or weight (V):

$$Ae_{t1-t2} = C \times V$$

If the concentration is < lower limit of quantification (LLOQ), the excretion will be assumed to be zero. For intervals in which no sample was collected (e.g., no defecation), the excretion will be assumed to be zero.

Cumulative excretions for each continuously sampled interval will be calculated by adding the excretions in the current and all previous collection intervals:

$$Ae_{0-t} = \sum_{i=1}^{n} \left(Ae_{t_{start} - t_{end}} \right)_{i}$$

The excretion rate ($\Delta Ae/\Delta t$) will also be calculated by dividing the excretion in each interval by the time difference in hours between the end and the start of the collection interval:

$$\frac{\Delta Ae}{\Delta t} = \frac{Ae}{t_{end} - t_{start}}$$

If a participant has not met the criteria for ending the collection of blood and excreta on Day 29 (i.e., end of confinement), cumulative excretion will be calculated up to and including the last continuous 24 hour visit during confinement. Interpolation will be used to estimate urinary and fecal excretion between confinement and 24 hour visits and between subsequent 24 hour visits, the midpoint method will be used to estimate Ae t_{start-tend}. The excretion rate of each collection interval will be plotted as a function of the midpoint of the respective interval. The area under this curve is Ae.

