3.5.1.1.2 Urine Collection

During the intervals defined in the schedule of assessments ([Table 1](#)), urine will be collected in urine containers for the analysis of GBT021601 and total radioactivity. Selected pooled urine samples will be used for metabolite identification.

The participants will be instructed to empty their bladders completely before study drug administration and at the end of each collection interval. A blank urine sample will be collected within 12 hours prior to study drug administration. The exact start and end times of urine collection and the urine weight of the entire interval (before and after addition of any urine stabilizers or additives) will be recorded in the eCRF; however the time of each void within the interval may not be recorded.

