3.6.2.1 Pharmacokinetic Evaluation

The PK parameters and their statistical evaluation will be included in the CSR for this study. All concentration data will be summarized using descriptive statistics and will be listed and summarized in tabular and/or graphical form. Missing PK data will not be imputed and any anomalous concentration values may be excluded from analysis at the discretion of the pharmacokineticist after review of available documentation. Any such exclusion will be discussed with the Sponsor’s clinical pharmacologist and clearly described in the CSR. Additional details about data analysis will be provided in the SAP.

Individual whole blood and plasma PK parameters will be determined for both total radioactivity and GBT021601. Individual CCI and urine PK parameters will be determined for GBT021601. Individual urinary and fecal excretion of total radioactivity over time will be determined. The ratio of whole blood to plasma for total radioactivity and GBT021601, and the ratio of CCI to plasma for GBT021601 will also be calculated. CCI and ratio with total radioactivity in whole blood/plasma will also be determined.

Summary statistics of PK parameters (primary and secondary) will be presented including number of participants, arithmetic means, geometric means, standard deviations, coefficients of variation, medians, and ranges (minimum, maximum). No inferential statistical analyses are planned.

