Appendix 4: Shells for Post-Text Tables, Figures and Listings	
19.0 Document History	

3.0 Introduction

This Statistical Analysis Plan (SAP) describes the statistical methods that will be used during the analysis and reporting of data collected under Global Blood Therapeutics (GBT), Inc., Protocol GBT021601-013.

This SAP should be read in conjunction with the clinical study protocol and electronic case report form (eCRF). This version of the plan has been developed using the protocol Version 3.0, dated 13-Mar-2023 (including all amendments up to this protocol date) and the final eCRF(s) dated 31-Oct-2022.

An approved and signed SAP is a requirement for database lock.

This SAP only covers the results that will be processed by the ICON Early Development Services (EDS) Biostatistics Department, Statistical Programming Department and Pharmacokinetic Department.

ICON EDS will perform the pharmacokinetic (PK), and safety and tolerability evaluation.

Metabolic profiling is not described in this SAP and will not be included in the corresponding TFLs. This SAP supersedes the statistical considerations identified in the protocol; where considerations are substantially different, they will be so identified. Any post-hoc or unplanned analyses, or significant changes from the planned analysis in this SAP performed to provide results for inclusion in the clinical study report (CSR) but not included in this SAP, will be clearly identified in Section 9.8.2 of the CSR. Changes to planned analyses do not require an updated SAP but should be included in the CSR if significant.

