9.1.2 Imputation

[figure not shown]
Unless otherwise noted, data will not be imputed. Imputation will only be used for:

- PK concentrations below the quantifiable limit (BQL) (see Section 16.1.2).
- PK amounts excreted will be interpolated between confinement and 24 hour visits and between subsequent 24 hour visits (see Section 16.1.2)
- Missing start or end date/times of AEs for the calculation of onset and duration (see Section 17.1.1).
- Missing adverse event (AE) severity, relationship and seriousness of AEs see Section 17.1.1).
- Safety laboratory data that are <x or >x (e.g. "<1.03", ">1000"): the analysis value or normal limit value will be the value of the detection limit itself plus or minus one precision unit for the parameter concerned (respectively 1.02 and 1001 in the example). The values before imputation ("<1.03", ">1000") will only be shown in listings. Listings will present the values before imputation.

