- o. Urine samples for PK of GBT021601 and total radioactivity will be collected on Day 1 (prior to dosing) and after dosing from 0 to 6 hours, 6 to 12 hours, 12 to 24 hours postdose, and thereafter in 24-hour intervals up to Day 29. Urine will also be collected in 24-hour intervals starting on Days 35 (816 hours postdose), 42 (984 hours), 56 (1320 hours), 70 (1656 hours), 84 (1992 hours), 98 (2328 hours), 112 (2664 hours), 136 (3240 hours), 150 (3576 hours), 178 (4248 hours), and 206 (4920 hours) in accordance with the applicable time windows (depending on if criteria for ending collection of blood and excreta are met see Footnote a, the collection may be ended prior to Day 206). Selected pooled urine will be used for metabolite identification.
- p. Fecal collections for the analysis of total radioactivity will be made at predose on Day -1, and complete collections will be made after dosing in 24-hour intervals up to Day 29. Feces will also be collected in 24-hour intervals starting on Days 35 (816 hours postdose), 42 (984 hours), 56 (1320 hours), 70 (1656 hours), 84 (1992 hours), 98 (2328 hours), 112 (2664 hours), 136 (3240 hours), 150 (3576 hours), 178 (4248 hours), and 206 (4920 hours) in accordance with the applicable time windows (depending on if criteria for ending collection of blood and excreta are met see Footnote a, the collection may be ended prior to Day 206). Participants will receive the appropriate containers to collect all feces at home within 24 hours prior to admission on Day -1 and each of the 24-hour stays. These fecal samples will be used if no feces is produced between admission on Day -1 and study drug administration (as a blank sample) or during the 24-hour stays after Day 29, respectively. Selected pooled fecal samples will be used for metabolite identification.
- q. Collection of vomitus for analysis of total radioactivity concentrations (if possible), if produced between dosing and 24 hours postdose.
- r. COVID-19 testing may be performed at the Investigator's discretion.

EDSREP 009 T 01 G Page 24 of 30

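### The SAP's zero for any interval without a sample also covers uncollected urine and missed stool, which can understate recovered radioactivity

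*SAP*

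**What the plan says.** SAP 16.1.2.2 covers urinary and fecal excretion together. Results below the LLOQ count as zero excretion. The next sentence adds: "For intervals in which no sample was collected (e.g., no defecation), the excretion will be assumed to be zero". The absence of a bowel movement is given only as an example; the rule is not confined to feces or to intervals in which nothing was produced.

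For participants followed after Day 29, the same section plots each collection interval's excretion rate at the interval midpoint and states: "The area under this curve is Ae".

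Four other places bear on the point:

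- SAP 9.1.2: "Unless otherwise noted, data will not be imputed. Imputation will only be used for" a list. For excreted amounts the list says "PK amounts excreted will be interpolated between confinement and 24 hour visits and between subsequent 24 hour visits". A zero for an uncollected interval is not on it.
- Protocol 3.6.2.1: "Missing PK data will not be imputed". The same section, and Protocol 3.7, leave further detail to the SAP; 3.7 names missing data expressly.
- SAP 3.0: "This SAP supersedes the statistical considerations identified in the protocol; where considerations are substantially different, they will be so identified". SAP 7.1 lists three changes (hemoglobin occupancy, the radioactivity assay schedule, the TEAE definition) and not this one.
- Protocol 3.5.1.1.2 has participants empty the bladder at the end of each interval and records this in the eCRF: "The exact start and end times of urine collection and the urine weight of the entire interval".

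**The concern.** The sentence treats two different things alike. A complete collection with no stool is an observed zero. A 24-hour urine interval with no sample is almost always a failed collection, because urine is produced every day; the same goes for a stool that was passed but not kept. Scoring these as zero can only lower the recovered amount.

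Mass balance is a primary objective. If excretion follows the 28 to 30 day half-life quoted for blood and plasma, about half of it falls after confinement and is estimated from at most 11 separate 24-hour visits. One false zero there stands in for days or weeks of excretion. It lowers Ae and fe for that route, and Ae_total and fe_total with them. Listing 16.2.6.2 may show the event, but the summary tables would still use the zero.

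**Working it through.** **The plan's own figures.** The administered radioactive dose, which is the denominator of fe, is 400 mL × 0.185 kBq/mL × 0.985 = 72.89 kBq, as SAP 16.1.2.3 states. The visit start times equal (day − 1) × 24 h for all 11 visits, for example Day 42: 41 × 24 = 984 h.

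**Inputs.** Half-life 28 to 30 days (Protocol synopsis; SAP 6.0). Continuous collection to 672 h (28 d), then 24-hour collections at the nominal visits (SAP Appendix 2, footnotes o and p). Linear trapezoid on rates at interval midpoints (SAP 16.1.2.2).

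**Assumptions, not in the documents.** The route's excretion is mono-exponential at the blood and plasma half-life, with no early unabsorbed fraction at first. Rate r(t) = k·exp(−kt), k = ln 2 / half-life, as a fraction of what the route eventually excretes. Relative losses then do not depend on the urine/feces split or on total recovery.

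**Full data.** Confinement contributes 1 − exp(−28k) = 50.0% (28 d) or 47.6% (30 d). The interpolated curve adds 49.9% or 52.0%. Totals: 99.9% and 99.6%.

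**One zero at Day 42.** Midpoints of Days 35, 42 and 56 are 34.5, 41.5 and 55.5 d, so the Day 42 point carries (55.5 − 34.5)/2 = 10.5 days of weight, not one day. With half-life 28 d, k = 0.02476 and r(41.5) = 0.00886. The loss is 0.00886 × 10.5 = 9.30%, and 9.30/99.9 = 9.3% of that route's Ae. A half-life of 30 d also gives 9.3%.

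| Visit set to zero | Weight (days) | Loss, % of route's Ae (28 to 30 d) | Change if omitted and interpolated, points |
|---|---|---|---|
| Day 35 | 7 | 7.3 to 7.4 | +0.1 |
| Day 42 | 10.5 | 9.3 | +0.2 to +0.3 |
| Day 56 | 14 | 8.8 to 9.0 | +0.5 |
| Day 84 | 14 | 4.4 to 4.7 | +0.2 to +0.3 |
| Day 178 | 28 | 0.9 to 1.1 | +0.2 |
| Day 206 | 14 | 0.2 to 0.3 | −0.6 to −0.8 (curve ends at Day 178) |

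**Early-excreted fraction.** If a fraction f of the route's output leaves early in confinement, only 1 − f follows the slow curve, and the Day 42 loss is about (1 − f) × 9.3%: 7.4% for f = 0.2, 5.6% for 0.4, 3.7% for 0.6.

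**Half-life range.** At 20 to 40 days, with no early fraction, the Day 42 and Day 56 losses lie between 7% and 10%.

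**During confinement.** A missed 24-hour interval after the first day costs its own amount, 1.2 to 2.4% at 28 to 30 d. If it is the last interval, it also lowers the starting point of the interpolation, by a further 3.7 to 3.8%.

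**Group mean.** At an assumed 50% urine share, full recovery and no early fraction, a Day 42 urine zero costs 9.3 × 0.5 = 4.65 points of dose in that participant: 4.65/10 to 4.65/8, or about 0.5 to 0.6 points, in the mean of 8 to 10 participants.

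**The case against.** Three stronger readings are tempting, and the documents do not support them.

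- *The zero rule breaches the protocol.* Protocol 3.6.2.1 bars imputation of missing PK data, but Protocol 3.7 leaves missing-data handling to the SAP, and SAP 3.0 gives the SAP precedence. SAP 9.1.2 allows exceptions noted elsewhere, and 16.1.2.2 can be read as one. Interpolation, the remedy proposed here, is itself listed as imputation in 9.1.2, so a strict reading of the protocol would bar it too. What stands is that the rule appears neither in the 9.1.2 list nor in 7.1.
- *An uncollected urine interval is never a true zero.* The collection-stopping criteria anticipate undetectable radioactivity, and results below the LLOQ score zero anyway. In late intervals the assigned zero may match what a sample would have given.
- *A missed visit will be scored as zero.* The sentence comes before the text on continuously sampled intervals, and the post-confinement method is a separate paragraph that interpolates between visits. A wholly missed visit can be read as a gap. The SAP does not say which reading applies. A sample collected and then lost is not literally within the rule either, and no rule is given for it.

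It is also fair that such events should be uncommon. Urine is collected during in-unit stays, and SAP Appendix 2, footnote p, lets a home stool sample stand in when none is produced "or during the 24-hour stays after Day 29, respectively". Protocol deviations are listed, the CSR must explain missing data, and the study is descriptive. The small interpolation error in the table partly reflects the smooth curve assumed. None of this makes zero the right value for a missing sample with measurable excretion.

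**Conclusion.** The point holds as a matter of scope: the rule is wider than the case that justifies it. Where excretion is still measurable, the direction of the error is certain, and it is downward. Its size is illustrative. If the rule is applied to a post-Day 29 visit, one Day 42 zero lowers that route's Ae by about 9.3% with no early-excreted fraction and by 3.7 to 7.4% with 60% to 20% excreted early; by Day 206 the effect is negligible. These figures rest on mono-exponential excretion at the blood and plasma half-life and on nominal visit times. The documents give neither the excretion half-life, nor the urine share, nor the frequency of missed collections. This should be fixed because it touches a primary objective and costs little, although the effect on the group mean from one event is small.

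**What to change.** In SAP 16.1.2.2, limit the zero to intervals with complete collection in which nothing was produced. Then state:

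- After Day 29, an uncollected or lost sample, or a missed visit, is missing. Omit that midpoint, interpolate between the nearest observed visits, and flag the participant.
- If the last visit is missing, report recovery to the last observed visit and give that time point. In the illustration this shortens the curve by 0.6 to 0.8 points.
- During confinement, flag the interval, and mark that participant's cumulative recovery as incomplete, rather than scoring zero.

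List the rule in SAP 9.1.2 and 7.1.

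The cost is a few sentences, a small programming change, and a per-interval marker that separates not collected from none produced. Urine times and weights are already in the eCRF. For stool, Protocol 3.5.1.1.3 records what was collected, not what was passed and missed, so a source check may be needed. No new samples are required. How the home stool sample enters the fecal rate is a separate matter that this change does not settle.
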